In a hypothesis testing research proposal, briefly mention the hypothesis to be tested and provide the scientific basis of the hypothesis, critically examining the observations leading to the formulation of the hypothesis.

Does this research proposal involve testing of hypothesis: \(\simega\) No \(\simega\) Yes (describe below)

The typhoid Vi-polysaccharide conjugate vaccine will be effective in preventing typhoid fever among Bangladeshi children.

Specific Objectives:

Describe the specific objectives of the proposed study. State the specific parameters, gender aspects, biological functions, rates, and processes that will be assessed by specific methods.

Primary objective:

To evaluate the effectiveness of typhoid conjugate vaccine (TCV) against blood culture-confirmed typhoid fever using the test-negative design

Secondary objective:

- To evaluate the effectiveness of typhoid conjugate vaccine (TCV) against blood culture-confirmed typhoid fever stratified by age groups (6 months to <2 years, 2 to 4 years, 5 to 15 years)
- To evaluate the effectiveness of typhoid conjugate vaccine (TCV) against blood culture-confirmed typhoid fever stratified by the period of follow-up (first and second six months) after vaccination
- To determine the immunogenicity of TCV in a subset of participants, stratified by age groups (6 months to <2 years, 2 to 4 years, 5 to 15 years)

Background of the Project including Preliminary Observations:

Provide scientific validity of the hypothesis based on background information of the proposed study and discuss previous works on the research topic, including information on sex, gender and diversity (ethnicity, SES) by citing specific references. Critically analyze available knowledge and discuss the questions and gaps in the knowledge that need to be filled to achieve the proposed aims. If there is no sufficient information on the subject, indicate the need to develop new knowledge.

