SOP and training																						
materials																						
development																						
Training for																						
vaccination and																						
surveillance																						
Listing of																						
interested children																						
for vaccination in																						
the study area																						
Vaccination																						
AEFI recording																						
SAE recording																						
and reporting																						
Diary card review																						
Patient enrollment																						
in the passive																						
surveillance																						
Patient																						
management																						
Sample collection																						
for imunogenicity																						
and passive																						
surveillance																						
Laboratory																						
analysis																						
Data cleaning																						
Development of																						
statistical analysis																						
plan																						
Data analysis																						
Clinical study																						
report (CSR)																						
development																						
Manuscript																						
writing and																						
submission																						
Dissemination of																						
findings in																						
national and																						
	 	1	1	 	 	l	l	l	1									1	1	1		

international											
community											

Sample Size Calculation and Outcome (Primary and Secondary) Variable(s)

Clearly mention your assumptions. List the power and precision desired. Describe the optimal conditions to attain the sample size. Justify the sample size that is deemed sufficient to achieve the specific aims.

A sample size of 515 (103 cases and 412 controls) will be required in this case-control test-negative design study assuming vaccine effectiveness of 80%, vaccine coverage of 65% in the target age-eligible population (6 months to 15 years), 4 controls per case, precision width of \pm 10% (20%) and type 1 error rate of 0.05. Considering the incidence rate for typhoid fever of 230 per 100,000 person-years among the non-vaccinated population aged 6 months to 15 years, the target number of vaccinations is \sim 60,000.

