For the evaluation of vaccine protection, a conditional logistic regression model will be used, considering matched case-control status as the outcome and vaccination status and selected covariates as independent variables, taking non-receipt of vaccine as the referent category for assessment of vaccine protection. Odds ratios for the associations between vaccination and typhoid fever will be estimated by exponentiation of the coefficient for vaccination from the fitted model, and the standard error of the coefficient will be used to calculate 95% confidence intervals for the estimated effect. Protective effectiveness will be calculated as $[(1 - \text{odds ratio}) \times 100\%]$. The threshold of statistical significance will be considered at P < 0.05.

Analysis of immunogenicity and safety data

Geometric Mean Titres (GMT) and seroconversion rate (≥4-fold rise of anti-Vi-IgG antibody titre induced on day 30 compared to day 0 before vaccination) of anti-Vi-IgG antibody titre will be calculated. Analysis of covariance will be used to adjust for imbalances in baseline titres.

In addition, descriptive analyses of safety data will be done for AEFI or SAEs cases.

Shell table for effectiveness of the typhoid conjugate vaccine against culture-confirmed typhoid cases

	Typhoid C	Cases	Matched c	ontrols	Vaccine effectiveness (VE) (95% CI)					
Overall period	Vaccinees n/N (%)	Non- vaccinees n/N (%)	Vaccinees n/N (%)	Non- vaccinees n/N (%)	Crude VE	P value	Adjusted VE	P value		
All ages	 	I	 	I	 	 		 		
6 months - <2 years										
2 - 4 years										
5 - 15 years										
First six months										
All ages										
Second six mont	hs									
All ages										

Data Safety Monitoring Plan (DSMP)

All clinical investigations (research protocols testing biomedical and/or behavioural intervention(s)) should include the Data and Safety Monitoring Plan (DSMP). The purpose of DSMP is to provide a framework for appropriate oversight and monitoring of the conduct of clinical trials to ensure the safety of participants and the validity and integrity of the data. It involves involvement of all investigators in periodic assessments of data quality and timeliness, participant recruitment, accrual and retention, participant risk versus benefit, performance of trial sites, and other factors that can affect study outcome.

Trial Monitoring

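### The only interval method stated for VE, coefficient and standard error, can leave the under-2 stratum, a named secondary objective, with no finite estimate or interval

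*Protocol*

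**What the plan says.** The Statistical analysis section of the protocol fits a conditional logistic regression to the matched sets, exponentiates the vaccination coefficient and takes VE as one minus the odds ratio. For the interval it says: "the standard error of the coefficient will be used to calculate 95% confidence intervals for the estimated effect". That is a Wald interval. The section names no alternative, minimum case count or exception.

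The secondary objectives ask for VE "stratified by age groups (6 months to <2 years, 2 to 4 years, 5 to 15 years"). The shell table has a row for "6 months - <2 years", with columns for crude and adjusted VE, 95% CI and P value. Its six-month period rows are for all ages only.

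The sample size section is built on the overall VE alone: "A sample size of 515 (103 cases and 412 controls) will be required", "assuming vaccine effectiveness of 80%, vaccine coverage of 65% in the target age-eligible population", with "4 controls per case". It gives one incidence figure for the whole age range and nothing specific to children under 2. The section on matching of cases and controls takes the age group at focal time, which the protocol defines as symptom onset. The cohort is closed: eligibility for surveillance depends on age on the first day of the campaign.

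**The concern.** In a closed cohort with age taken at symptom onset, children leave the under-2 group during follow-up and none replace them. The stratum is therefore likely to hold few cases. If VE is near 80%, most of those cases will be unvaccinated, and there may be no vaccinated case in any set that contributes to the conditional likelihood.

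The fitted coefficient then runs to minus infinity. Software would show VE of 100% with a meaningless standard error, an unusable interval and a Wald P value near 1, although the data favour the vaccine. The failure becomes more likely as the vaccine works better. A valid lower confidence limit could be had from the same data by another method.

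**Working it through.** **1. The plan's own figure.** Inputs from the sample size section: VE 80% (OR 0.20), coverage 65%, four controls per case, total CI width 20 points, alpha 0.05.

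- Vaccinated share among cases: p1 = 0.65 × 0.20 / (0.35 + 0.65 × 0.20) = 0.13/0.48 = 0.2708.
- Variance of log OR times n: 1/(0.2708 × 0.7292) + 1/(4 × 0.65 × 0.35) = 5.064 + 1.099 = 6.163.
- Half-width x on the log scale: 0.20 × (e^x − e^−x) = 0.20, so x = 0.4812.
- n = 6.163 × (1.96/0.4812)² = 102.2, rounded up to 103 cases, hence 412 controls and 515 in total. The stated figure reproduces.

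**2. Expected yield in a year.** About 92,000 eligible, about 60,000 vaccinated, and "incidence rate for typhoid fever of 230 per 100,000 person-years among the non-vaccinated population aged 6 months to 15 years": 32,000 × 0.0023 + 60,000 × 0.0023 × 0.20 = 73.6 + 27.6 = 101.2 cases.

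**3. Under-2 share.** *Assumed here, not stated in the protocol: uniform ages from 0.5 to 16.0 years (15.5 age-years), equal incidence and equal coverage at all ages.* At t years after the start, the under-2 group spans 1.5 − t years, an average of 1.0 over 12 months.

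| Reading | Share | Cases of 101.2 |
|---|---|---|
| Age at symptom onset, months 0–12 | 1.0/15.5 = 6.5% | 6.5 |
| Same, counting from day 14 | 6.3% | 6.4 |
| Same, counting starts 3 months after the age cut | 4.8% | 4.9 |
| Age at vaccination | 1.5/15.5 = 9.7% | 9.8 |

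The protocol places the highest incidence at 5–9 years. If incidence is lower under 2, the count falls further. A range of 3 to 10 is used below.

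**4. Chance of no finite estimate.** A set informs the conditional likelihood only if its members differ in vaccination status.

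- Vaccinated case, at least one unvaccinated control: a = 0.2708 × (1 − 0.65⁴) = 0.2225.
- Unvaccinated case, at least one vaccinated control: b = 0.7292 × (1 − 0.35⁴) = 0.7182.
- The estimate is finite only if both kinds of set occur. With N cases, P(not finite) = (1 − a)^N + (1 − b)^N − (1 − a − b)^N.
- At N = 6: 0.7775⁶ + 0.2818⁶ − 0.0593⁶ = 0.2209 + 0.0005 − 0.0000 = 0.221. Nearly all of it comes from having no vaccinated case in an informative set.

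| Under-2 cases | Fixed count | Poisson count with that mean |
|---|---|---|
| 3 | 49% | 57% |
| 5 | 29% | 35% |
| 6 | 22% | 27% |
| 8 | 13% | 17% |
| 10 | 8% | 11% |

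Simulating the 1:4 conditional likelihood agrees (21.8% at a fixed 6). At 6 cases, true VE of 70% gives 13% and 90% gives 44%.

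**5. When the estimate is finite.** At about 6 cases the simulated Wald interval for VE has median limits of about −80% and 96%, and covers the true value in about 97% of those trials.

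**6. What the stated method discards.** I simulated 6 cases and kept the trials with no vaccinated case in an informative set. The exact conditional 95% lower limit for VE has a median of about 29% and exceeds zero in 79% of them. With mid-P the figures are about 46% and 93%. At 3 cases little can be recovered: the exact limit exceeds zero in about 6% of failing trials.

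**7. The other rows.** Ages 2–4 hold about 3/15.5 × 101.2 = 19.6 cases; at 20 cases the failure chance is 0.7%. Each six-month period holds about 50 cases, where it is below 0.001%. The all-ages analysis, with about 28 vaccinated cases, is not at risk.

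**The case against.** The strongest objection is that handling a sparse stratum is ordinary SAP content. The study timeline lists an SAP as a separate activity, and the interval sentence is a general description that does not say it governs every estimate. This stands in part: an SAP not shown here may hold a fallback. But the protocol does not leave the method open. It names one and sets out a table row in which that method can fail, so the protocol wording itself needs the qualification.

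A second objection also stands. The protocol gives no under-2 count, and although it fixes focal-time age for matching, neither the secondary objective nor the shell table says which age defines the analysis strata. Age at vaccination would give about 10 cases and a risk of 8–11%. No single headline figure is supported.

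A third is that the shell table prints vaccinated and non-vaccinated counts beside each VE, so a zero would be visible. That reduces the risk of misreading but does not supply an interval.

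Two stronger readings are tempting and not supported. A reader might infer that the Wald interval under-covers, because at 6 cases only about 76% of all trials yield a finite interval containing the truth. That figure is 0.78 × 0.97, the 22% failure chance counted again. A reader might also infer that all VE results are at risk; step 7 shows they are not.

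**Conclusion.** The point holds for the 6 months to <2 years stratum only. The stated method has an appreciable chance of giving no finite VE or interval there: about 22% at 6 cases, with a plausible range from 49% at 3 cases to 8% at 10 (27%, 57% and 11% if the count is Poisson).

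These figures assume VE 80%, coverage of 65% in this age group, four controls per case, and matched controls whose vaccination is independent of the case's. The case counts further assume uniform ages and equal incidence. Higher true VE or lower under-2 incidence makes failure more likely; defining the strata by age at vaccination makes it less likely. When an estimate is obtained, the interval is very wide but does not under-cover. The consequence is confined to a secondary objective.

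**What to change.** In the Statistical analysis section, keep the interval based on the standard error for the all-ages and six-month period analyses. For the age strata, prespecify one of:

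- exact conditional logistic regression, with a median-unbiased estimate and an exact or mid-P interval; or
- Firth-penalised conditional likelihood with a profile-likelihood interval.

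Apply it either to all age strata or under a rule fixed before vaccination status is seen and tied to sparsity, for example no or very few vaccinated cases in informative sets. A loose trigger would switch method often in the 2–4 year stratum, where failure is rare. It would also help to say whether the strata use age at symptom onset or at vaccination, and to give the expected cases per stratum.

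The cost is a sentence or two of wording and slightly more analysis work in standard software, with no extra data. Exact intervals are somewhat conservative, and no method will make an estimate from 3 to 10 cases precise. Settling the choice now avoids picking a method after a result of 100% has been seen.
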